### 9.3 Other Endpoints

1) Serum influenza antibody titer

This endpoint is defined as the ratio of value on Day 22 to that on Day 1.

2) Polymorphic and treatment-emergent amino acid substitutions in the PA gene of evaluable virus

This endpoints is defined as follows:

- The percentage of samples which have polymorphic amino acid substitutions on Day 1 compared to the reference sequence
- The percentage of samples which have treatment-emergent amino acid substitutions between Day 1 and the time point when last positive RT-PCR is obtained

For treatment-emergent amino acid substitutions in the PA gene, sequencing data obtained at the baseline (Day 1) and last RT-PCR positive timepoint will be compared for treatment-emergent amino acid substitutions in the PA gene in the S-033188 group and placebo group, respectively.

For polymorphic amino acid substitutions in the PA gene, sequencing data obtained at the baseline (Day 1) will be compared to that of the reference sequence in the S-033188 group and the placebo group, respectively.

The patients who have sequencing performed will be included in this analysis.

3) Drug susceptibility in patients with evaluable virus (unit: EC50 nM, IC50 nM)

This endpoints is defined as follows:

- EC50 for S-033447 at baseline
- IC50 for oseltamivir at baseline
- The ratio of EC50 for S-033447 relative to EC50 for reference stain
- The ratio of IC50 for oseltamivir relative to IC50 for reference stain

If the EC50 is less than the lower limit, the EC50 will be imputed the lower limit

value (0.03 nM). If the EC50 is greater than upper limit, the EC50 will be imputed as the value of upper limit (1000 nM).

If the IC50 is less than the detection limit, the IC50 will be imputed detection limit value (0.01 nM). If the IC50 is greater than upper limit, the IC50 will be imputed as the value of upper limit (10000 nM).

The patients with a detected value at baseline will be included in this analysis. However, the patients infected with multiple virus types will be excluded from this analysis.

#### 4) EQ-5D-5L and EQ VAS

These endpoints consist of the change from baseline in the index value calculated from the EQ-5D-5L questionnaire and that in EQ VAS score on Day 1, 2, 3, 4, 5, 6, 7, 8, 9, 10, 11, 12, 13, 14 and 22. The index value will be recorded twice daily (morning and evening) from Day 1 to Day 9, and once daily (evening) from Day 10 to 14, and Day 22. A conversion table proposed by Ikeda et al. (2015) [1] will be used to convert EQ-5D-5L status to index value.

The EQ-5D-5L and EQ VAS data obtained when e-diary is set up after initial administration will not be used for analysis. Because these data may be observed due to e-dairy system's incorrect setting. In addition, the EQ-5D-5L and EQ VAS data observed in the evening after Day 15 will be excluded from this analysis. Because these data may be observed at unplanned time point in the protocol due to e-dairy system's incorrect setting. Only if evening data observed on the last visit date but no data whose timepoint is 'Visit' are collected, the data will be included in the analysis.

#### 5) Work productivity (WP) questionnaire

The WP questionnaire consists of 4 questions regarding employment, hours worked, productivity while at work, and requirement for personal assistance. The following 2 endpoints are derived from Q1 to Q3 questions.

The percentage of absenteeism due to influenza illness is defined as follows;

$100 \times (\text{duration unable to work due to influenza illness: Q2}) / (\text{duration of working per 21 days: Q1} \times 21 \text{ days} / 7 \text{ days})$  (unit: %)

The patients whose Q1 and Q2 were observed with the same unit will be included in this analysis.

The percentage of work productivity loss due to influenza illness is defined as follows;

$100 \times \{(\text{duration unable to work due to influenza illness: Q2}) + (\text{duration of working below normal standard: Q3})\} / (\text{duration of working per 21 days: Q1} \times 21 \text{ days} / 7 \text{ days})$  (unit: %)

The patients whose Q1, Q2 and Q3 were observed with the same unit will be included in this analysis.

6) Intrahousehold infection rate (for Japan site only)

Intrahousehold infection rate in each patient is defined as follows

$100 \times (\text{the number of household members infected between Day 1 and Day 15}) / \{(\text{the number of household members, excluding the patient him/herself}) - (\text{the number of household members infected by Day 1})\}$  (unit: %)

The patients who have no household members or whose all household members has already been infected by Day 1 will be excluded from the analysis population.

When a part of the date of influenza diagnosis is observed for a household member, he/she is defined as a influenza case in household. If any part of the date of his/her influenza diagnosis is missing, he/she will be diagnosed between Day 1 and Day 15.

For each of the following time periods, definition of this endpoint will be defined as below.

- $100 \times (\text{the number of household members infected between Day 1 and Day 3}) / \{(\text{the number of household members, excluding the patient him/herself}) - (\text{the number of household members infected by Day 1})\}$  (unit: %)
- $100 \times (\text{the number of household members infected between Day 1 and Day 4}) / \{(\text{the number of household members, excluding the patient him/herself}) - (\text{the number of household members infected by Day 1})\}$  (unit: %)
- $100 \times (\text{the number of household members infected between Day 1 and Day 6}) / \{(\text{the number of household members, excluding the patient him/herself}) - (\text{the number of household members infected by Day 1})\}$  (unit: %)
- $100 \times (\text{the number of household members infected between Day 1 and Day 11}) / \{(\text{the number of household members, excluding the patient him/herself}) - (\text{the number of household members infected by Day 1})\}$  (unit: %)

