Appendix 2 QOL Questionnaire (EuroQol-5 Dimensions–5 Levels)

Appendix 3 Work Productivity (WP) Questionnaire

Work Productivity Questionnaire cover note:

To the investigator:

This questionnaire is designed to capture the impact of influenza symptoms on patients' ability to work and perform normal activities. We would like the patient to complete the questionnaire once, during the clinic visit following resolution of their symptoms

[figure not shown]
1. How many hours or days per week do you work (e.g., full or part time paid work, voluntary work, or studying)?
2. Due to your recent influenza illness, for how many hours or days were you unable to work? ___ hours, or ___ days
3. Due to your recent influenza illness, for how many hours or days did you feel that your symptoms caused you to perform below your normal standard even though you attended work? ___ hours, or ___ days
4. Due to your recent influenza illness, for how many hours or days did you require someone to help you with your normal activities? ___ hours, or ___ days

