- The summary statistics for change in the index value and change in VAS score will be presented by treatment group at each scheduled time point.

5) Work Productivity Questionnaire

- The summary statistics for the percentage of absenteeism due to influenza illness and the percentage of work productivity loss due to influenza illness will be presented by treatment group.
- For Question 4 in Work Productivity (WP) Questionnaire, the summary statistics for the number of days required for personal assistance will be presented by treatment group. One day is equal to 24-hours.

6) Intrahousehold infection rate

Let  $K$  be the total number of patients included in this analysis,  $y_k$  be the number of  $k^{\text{th}}$  patient's household members infected between Day 1 and Day 15, and  $n_k$  be the number of  $k^{\text{th}}$  patient's household members uninfected by Day 1 ( $k = 1, \dots, K$ ). Under the assumption that  $y_k$  is distributed according to Poisson distribution with mean  $\mu_k$ , the following Poisson regression model will be applied;

$$\log(\mu_k) = \log(n_k) + \beta_0 + \beta_1 x_k$$

In the model,  $x_k$  is a group indicator variable for the  $k^{\text{th}}$  patient, i.e.,  $x_k = 1$  for the S-033188 group,  $x_k = 0$  for the control group (the placebo group or the oseltamivir group). The  $\beta_0$  is an intercept parameter,  $\beta_1$  is a regression parameter. Intrahousehold infection rates for the S-033188 group and the control group are given by  $\exp(\beta_0 + \beta_1)$  and  $\exp(\beta_0)$ , respectively. Estimate and 95% CI of intrahousehold infection rate of each treatment group and comparison between two treatment groups will be carried out using the following SAS code. In addition, a risk ratio of the S-033188 group to the control group and the corresponding 95% CI will be estimated by the above Poisson regression model.

```
Data analysisdata;  
  set analysisdata;  
  lnum=log(NUM);  
run;
```

[Comparison between the S-033188 group and the placebo group]

```
proc genmod data = analysisdata;  
  class TRTP;  
  model RES = TRTP / dist = poisson link = log offset = lnum;  
  lsmeans TRTP / cl exp;  
  estimate "S-033188 vs Placebo" TRTP 1 -1 / exp;  
run;
```

- NUM: Number of household members uninfected by Day 1
- TRTP: Treatment group (1:S-033188, 2:Placebo)
- RES: Number of household members infected between Day 1 and Day 15

[Comparison between the S-033188 group and the Oseltamivir group]

```

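### Work-productivity questionnaire: Q4 pools hour and day answers at 24 hours per day, and the same-unit rule for Q1 to Q3 can make inclusion depend on the work lost (minor)

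*SAP*

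**What the plan says.** Protocol Appendix 3 offers both units throughout. Q1 asks "How many hours or days per week do you work", Q2 asks "for how many hours or days were you unable to work? ___ hours, or ___ days", and Q4 asks "for how many hours or days did you require someone to help you with your normal activities? ___ hours, or ___ days". Q3, on working below normal standard, has the same two boxes. Protocol 9.13.4.2 leaves variables and methods to the SAP.

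SAP 9.3, Other Endpoints, item 5 defines two percentages. Absenteeism is Q2 over a denominator described as "duration of working per 21 days: Q1", scaled by 21/7. Productivity loss puts Q2 plus Q3 over the same denominator. The inclusion rules are "The patients whose Q1 and Q2 were observed with the same unit will be included in this analysis" for absenteeism and "The patients whose Q1, Q2 and Q3 were observed with the same unit will be included in this analysis" for productivity loss. No conversion is given for mixed units.

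SAP 9.5 item 5 treats Q4 differently: "the number of days required for personal assistance will be presented by treatment group. One day is equal to 24-hours".

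SAP Table 3 assigns the questionnaire summary statistics only.

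**The concern.** The two rules fail in different ways.

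**Q4.** A 24-hour day suits elapsed time, such as time to cessation of viral shedding in SAP 9.2. Time spent being helped with normal activities is not elapsed time. Someone helped for some hours on each of three days can reasonably write 3 in the days box, or the total in the hours box. The SAP puts both into one mean on incompatible scales, so the summary depends on which box patients happened to use.

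**Q1 to Q3.** Inclusion turns on the unit of Q2 and Q3, which are outcome answers given after treatment. If short losses tend to be written in hours and long ones in days, the rule removes small losses from patients who gave Q1 in days, and large losses from patients who gave Q1 in hours. The share kept could then differ by arm when the loss does. The objective in Protocol 2.6 and SAP 3.6 is to compare the arms, so readers will compare these means even without a test. The work-productivity text plans no count of mixed-unit exclusions by arm and no sensitivity analysis.

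**Working it through.** The plan states no numerical target for this endpoint, so there is no figure to reproduce. The SAP formulas are applied directly.

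**Inputs from the documents**
- Hours or days for each question: Protocol Appendix 3.
- Absenteeism = 100 × Q2 / (3 × Q1), because 21/7 = 3: SAP 9.3 item 5.
- Q4 in days = hours / 24: SAP 9.5 item 5.
- Hours in a working day, or in a day of help: neither collected nor stated. Values below are assumptions.

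**Step 1: Q4**

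| Help on one day | Hours box | Days box | Ratio |
|---|---|---|---|
| 4 h | 4/24 = 0.17 | 1 | 6 |
| 6 h | 6/24 = 0.25 | 1 | 4 |
| 8 h | 8/24 = 0.33 | 1 | 3 |
| 12 h | 12/24 = 0.50 | 1 | 2 |
| 24 h | 24/24 = 1 | 1 | 1 |

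Three days with 8 hours of help each score 24/24 = 1.0 day or 3.0 days.

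**Step 2: who is kept for absenteeism**
- Q1 = 5 days, Q2 = 2 days: kept, 100 × 2/15 = 13.3%.
- Q1 = 40 hours, Q2 = 16 hours: kept, 100 × 16/120 = 13.3%.
- Q1 = 5 days, Q2 = 4 hours: dropped. With H hours per working day the value would be 100 × (4/H)/15, which is 3.3% at H = 8 and runs from 6.7% (H = 4) to 2.7% (H = 10).
- Q1 = 40 hours, Q2 = 3 days: dropped. The value would be 100 × 3H/120, which is 20% at H = 8, 15% at H = 6 and 25% at H = 10.

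**Step 3: how much the same-unit rule could matter**

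An illustrative simulation, with every distribution assumed: days lost are gamma with shape 1.2 and arm means of 1.5 and 2.25; the working week is 5 days, so the true values are 10.0% and 15.0% and the difference is 5.0 points. Q2 is given in hours for 90% of losses under one day and for 20% of longer ones, except that a stated share of patients simply reuse their Q1 unit.

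| Q1 in days | Reuse Q1 unit | Kept, by arm | Analysed means | Difference |
|---|---|---|---|---|
| 20% | 0% | 51%, 46% | 7.5% v 11.5% | 4.1 |
| 50% | 0% | 50%, 50% | 10.0% v 15.0% | 5.0 |
| 80% | 0% | 49%, 54% | 12.7% v 17.9% | 5.2 |
| 20% | 50% | 76%, 73% | 9.1% v 13.9% | 4.8 |
| 80% | 50% | 74%, 77% | 10.9% v 16.0% | 5.1 |
| any | 100% | 100%, 100% | 10.0% v 15.0% | 5.0 |

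Differences are taken before rounding. With no reuse of the Q1 unit, the arm means move by 2.5 and 3.5 points down, by nothing, or by 2.7 and 2.9 points up.

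These rows are not bounds. In a second set of assumptions (shape 1.5, means 2.0 and 2.5 days, true values 13.3% and 16.7%), suppose everyone gives Q1 in hours and every loss of a day or more in days. Then only 32% and 25% are kept, the means are 3.6% and 3.7%, and the 3.3-point difference falls to 0.1. If instead everyone gives Q1 in days, 68% and 75% are kept, with means of 17.8% and 20.9%. Both are corner cases.

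**The case against.** The same-unit rule has a rationale. Hours per working day are not collected, and Q1 covers part-time work, voluntary work and study in a trial that enrols from age 12. Any conversion adds error: a patient working five 4-hour days who loses 4 hours has truly lost 6.7%, but scores 3.3% at 8 hours per day. This stands, and it is why conversion belongs beside the same-unit analysis with a wide range.

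The four questions share one form and the same choice of boxes, so many patients may use one unit throughout, and then nothing is lost. This also stands. A reader might infer that inclusion does depend on the loss, or that about half of patients will be dropped. The documents support neither: they give no unit frequencies, and the 50% figure comes from assuming that the Q2 unit is chosen without regard to Q1. Even then, the difference between arms barely moves in two of the three cases.

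The exclusions will be partly visible, because SAP 6.1 reports the number of non-missing observations and lists all subject data. That shows how many were analysed, but not why the others were not.

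None of this rescues Q4. That its 24-hour rule is explicit does not make the two boxes comparable. Nor would an 8-hour working day be a grounded substitute for help at home: 6 hours would still score 0.75 against 1.

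**Conclusion.** The point holds as a minor one.

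For Q4, the discrepancy is arithmetic: the same help scores 2 to 6 times higher in days than in hours when it takes 12 to 4 hours of a day. The only premise is that a day of help need not mean 24 hours. How far the pooled mean is affected depends on the mix of boxes used, which is unknown.

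For Q1 to Q3, the exposure is real but its size and direction are unknown. It runs from no effect, if patients keep one unit, to roughly half of patients dropped and arm means shifted by up to about 3 points, if the Q2 unit is independent of the Q1 unit and follows the loss. More extreme answering habits would do more. The claim is that inclusion can depend on the outcome, not that it will, and no direction favouring either arm can be asserted.

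A reader might also infer a conflict between protocol and SAP, or a threat to the trial's conclusions. There is neither. The protocol delegates the method to the SAP, and this is an other endpoint with summary statistics and no test.

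**What to change.** In SAP 9.5 item 5, remove the 24-hour conversion for Q4 and summarise hour answers and day answers in separate rows by treatment group, with the number in each.

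In SAP 9.3 and 9.5, keep the same-unit analysis of Q1 to Q3 and show beside it an analysis that includes mixed-unit patients under a stated number of hours per working day. For example, use 8 hours, repeated over 4 to 10 hours to cover part-time work and study. Report the number excluded for mixed units by arm, separately for the two percentages.

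The cost is some SAP wording, a few lines of code and extra table rows. The downside is a conversion assumption that adds some measurement error; the range shows how much it matters. No change to the questionnaire or to data collection is needed.

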7.4.3 Intrahousehold Infection Rate

For sites in Japan only, patient will be interviewed predose at Visit 1 (Day 1) about their household size, the number of household members infected this season before the patient is enrolled the study and their diagnosis date (if the date is within 2 weeks) of influenza. From Day 1 to Day 15, the patient will be interviewed about the number of household members infected and their diagnosis date of influenza to evaluate the intrahousehold infection rate.

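### The SAP's incomplete-date rule for household cases has no exception for members already reported before dosing, so some pre-treatment infections would count as post-treatment ones.

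*SAP*

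**What the plan says.** Protocol 7.4.3 sets out two collections at Japanese sites. Before dosing at Visit 1, the patient gives the household size and a count of those at home who were "infected this season before the patient is enrolled the study and their diagnosis date (if the date is within 2 weeks) of influenza". After dosing, further interviews up to Day 15 record new household cases and when each was diagnosed. Protocol 9.13.5 leaves the definition and the analysis of the endpoint to the SAP.

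SAP 9.3, item 6, divides the members infected between Day 1 and Day 15 by the members other than the patient, less "the number of household members infected by Day 1". It adds an exclusion: "The patients who have no household members or whose all household members has already been infected by Day 1 will be excluded from the analysis". Two consecutive sentences then deal with dates. The first says who counts as a case: "When a part of the date of influenza diagnosis is observed for a household member, he/she is defined as a influenza case in household". The second says where a case goes when the date is incomplete, and it sets no condition on the interview or on the known part: "If any part of the date of his/her influenza diagnosis is missing, he/she will be diagnosed between Day 1 and Day 15".

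SAP 9.5, item 6, fits a Poisson model with a log offset defined by "NUM: Number of household members uninfected by Day 1". It reports rates, a risk ratio and confidence intervals against placebo and against oseltamivir.

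**The concern.** The endpoint is meant to show onward spread after treatment starts, so it must separate infections before Day 1 from those after it. The predose interview does this by its timing: nobody reported there can be a post-treatment case. The SAP's date rule does not use that fact. It asks only whether the date is complete.

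Two things are at stake:

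- **Numerator.** A pre-treatment case with a partial date is counted as spread from the treated patient.
- **Denominator, offset and exclusion.** These all need the number infected by Day 1, and the SAP names no source for it. The Visit 1 count includes members infected earlier in the season. A number built from dates would miss those for whom the protocol asks no date.

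**Working it through.** The documents give no expected rate, event count or power for this endpoint, so there is no planned figure to reproduce. The check applies the rules to cases and then gives a sensitivity calculation under stated assumptions.

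**Step 1: a partial date that lies wholly before Day 1.** The patient is enrolled and dosed on 5 January. The 2-week window of Protocol 7.4.3 reaches back to 22 December, so a date is requested for a member diagnosed in the last days of December. The patient knows the month but not the day. Part of the date is observed, so the member is a case. Part is missing, so the member is placed in Day 1-15, which is 5 to 19 January. No day in December can fall there.

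**Step 2: a partial date that fits both periods.** The patient is enrolled and dosed on 20 January. A member is reported predose as diagnosed in January, day unknown. Day 1-15 runs from 20 January to 3 February, so the month alone decides nothing. The interview decides it: the report came before dosing. A check on the known part of the date is therefore not enough without a check on which interview reported the case.

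**Step 3: effect in one household.** Assume three other members, one infected before Day 1 and no new case.

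| Treatment of the earlier case | Rate |
|---|---|
| Infected by Day 1 | 0/2 = 0% |
| Moved to Day 1-15, kept at risk | 1/3 = 33.3% |
| Moved to Day 1-15, also removed through the Visit 1 count | 1/2 = 50% |

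**Step 4: effect on the risk ratio.** Let e be the share of members who are predose cases moved to Day 1-15. They were reported before dosing, so e is equal across arms in expectation. With true rates pT and pC:

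Apparent ratio = (e + (1 - e) pT) / (e + (1 - e) pC)

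Assume pC = 10% and pT = 7%, a true ratio of 0.70.

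| e | Control rate | S-033188 rate | Ratio |
|---|---|---|---|
| 0.5% | 0.005 + 0.995 × 0.10 = 10.45% | 0.005 + 0.995 × 0.07 = 7.47% | 0.71 |
| 1% | 0.01 + 0.99 × 0.10 = 10.9% | 0.01 + 0.99 × 0.07 = 7.93% | 0.73 |
| 2% | 0.02 + 0.98 × 0.10 = 11.8% | 0.02 + 0.98 × 0.07 = 8.86% | 0.75 |

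Removing the moved cases from the denominator divides both rates by (1 - e), so the ratio does not change.

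**Step 5: the denominator ambiguity.** Suppose instead that a share u of members are undated earlier cases, not counted as new cases but left at risk. The rates become (1 - u) pC and (1 - u) pT. With u = 5% these are 0.95 × 10% = 9.5% and 0.95 × 7% = 6.65%. Both rates fall and the ratio stays at 6.65/9.5 = 0.70. This error runs the opposite way from Step 4 on the rates and has no expected effect on the ratio.

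**The case against.** A reader might infer something stronger: that every member infected earlier in the season becomes a secondary case, because the protocol takes no date for infections more than 2 weeks before enrolment. The documents do not support this. The first of the two SAP sentences makes someone a dated case only when part of the date is observed, and the second refers back to that person. A member with no date does not reach the Day 1-15 rule unless the second sentence is read alone. Nor does a December diagnosis serve as an example for a patient enrolled on 20 January. It would be at least 20 days old, and the protocol asks for no date that far back.

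The earlier cases also have a place of their own. The Visit 1 count needs no date, and the formula subtracts those infected by Day 1. A natural reading is that the Visit 1 count feeds the denominator and the later interviews feed the numerator. On that reading the ambiguity in Step 5 disappears.

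These points limit the affected group to members reported predose with a partial date. They also rule out large assumed shares: moving 5% or 10% of all members would describe earlier-season cases in general, which the rule does not reach. They do not remove the error in Steps 1 and 2. The SAP neither limits the date rule to members first reported after dosing nor says that the Visit 1 count overrides it.

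It is also fair that the endpoint is of low rank. The protocol synopsis lists it as secondary, but SAP Table 3 puts it among the other endpoints. It is collected in Japan only, and the hierarchical procedure in SAP 6.2 covers only the primary endpoint.

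**Conclusion.** The point holds in a limited form. Applied as written, the date rule counts a predose-reported member with a partial date as infected after treatment start, even when the known part rules that out. This inflates the rates and pulls the risk ratio toward 1. It creates no apparent benefit in expectation. Separately, the source of the number infected by Day 1 is not stated. If it were taken from dates, the rates would be too low and the ratio about unchanged.

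The size cannot be derived from the documents. The ratios of 0.71 to 0.75 in Step 4 rest on assumed true rates of 10% and 7% and on assumed shares of 0.5% to 2%. They show direction and scale only. The affected group is narrow, so the real effect is probably small. This is a minor correction.

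**What to change.** Amend SAP 9.3, item 6, before unblinding:

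1. Class every household member reported at the predose Visit 1 interview as infected by Day 1, whatever the date. Take this number from the Visit 1 count, and use it for the denominator, the Poisson offset and the exclusion of households with nobody left at risk.
2. Apply the Day 1-15 placement only to members first reported after dosing, and only when the known part of the date is compatible with Day 1-15.

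The cost is a few sentences and a small programming change. Protocol 7.4.3 already plans the predose count and the later interviews, so no new data are needed, provided that the database shows which interview first reported each member. The change leaves the SAP's requirement of at least a partly observed date for a post-dose case as it stands.
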